### 23. MULTI-CENTER GUIDELINES

#### 23.1. **Study Documentation**

Each participating site is responsible for submitting copies of all relevant regulatory documentation to the Coordinating Center. The required documents include, but are not limited to the following: local IRB approvals (i.e., protocol, consent form, amendments, patient brochures and recruitment material, etc.), each participant's informed consent, enrollment form, eligibility checklist and tissue block registration, summary of unanticipated problems or protocol deviations. and documentation of expertise of the investigators. The Coordinating Center will provide each participating site with a comprehensive list of the necessary documents. It is the responsibility of the participating sites to maintain copies of all documentation submitted to the Coordinating Center.

The requirements for data management, submissions, and monitoring are outlined below. The participating sites will submit all the research related information (source documents and research records – IRB approval documents, patient registration list, CRF info, toxicity assessments, tumor measurements/ responses, etc.) within 2 weeks of the patient's visit to the assigned Coordinating Center Monitor. The Coordinating Center Monitor will check if data was entered into Oncore within 1 week of receiving the information. Personnel from the VICC Clinical Trial Shared Resource will monitor the trial and may periodically visit the investigative site to assure proper conduct of the trial and proper collection of the data. The investigators at other sites will allow the monitor to review all source documents used in the preparation of the case reports.

#### 23.2. **Records Retention**

U.S. FDA regulations (21 CFR §312.62[c]) require that records and documents pertaining to the conduct of this study and the distribution of investigational drug, including CRFs, consent forms,

laboratory test results, and medication inventory records, must be retained by each Principal Investigator for 2 years after marketing application approval. If no application is filed, these records must be kept 2 years after the study is discontinued and the U.S. FDA and the applicable national and local health authorities are notified.

Following closure of the study, each participating center will maintain a copy of all site study records in a safe and secure location. The Coordinating Center will inform the investigator at each site at such time that the records may be destroyed.

#### 23.3. **Publication**

It is understood that any manuscript or releases resulting from the collaborative research will be circulated to all participating sites prior to submission for publication or presentation.

Any formal presentation or publication of data from this trial may be published after review and comment by Genentech and prior to any outside submission. Genentech will receive copies of any intended communication in advance of publication (at least twenty-one working days for presentational materials and abstracts and thirty working days for manuscripts). Principal Investigator/Institution shall have the final authority to determine the scope and content of its publications, provided such authority shall be exercised with reasonable regard for the interests of Genentech and, in accord with the trial contract shall not permit disclosure of Genentech confidential or proprietary information.

### 24. STATISTICAL CONSIDERATIONS

This two-part study consists of 1) a Phase Ib dose-escalation study of Idasanutlin in combination with Atezolizumab to determine an RP2D in patients with TP53-wt ER+ mBC, followed by 2) a Phase II open-label, multi-arm, multicenter clinical trial to determine whether whether Cobimetinib or Idasanutlin in combination with Atezolizumab improves anti-tumor effect relative to a historical control of Atezolizumab alone in patients with ER+ mBC.

#### Phase Ib Trial of Idasanutlin and Atezolizumab 24.1.

For the dose-escalation study, a standard 3 + 3 dose escalation scheme will be utilized to evaluate the primary objective of determining a RP2D (Recommended Phase II Dose) for Idasanutlin in combination with Atezolizumab. Three dosing cohorts of Idasanutlin will be evaluated in combination with Atezolizumab (dosage will be held constant at 840 mg) to determine the RP2D and will occur in accordance with the dose escalation rule below.

1 Cycle = 28 days			
N of pts.	Dose Level	Atezolizumab (IV q15 days)	Idasanutlin (PO daily x 5 out of 28 days)
3-6	3	840 mg	200 mg
3-6	2	840 mg	150 mg
3-6	1	840 mg	100 mg
3-6	-1	840 mg	50 mg

DLTs are defined in section 7.5 and will be assessed during a DLT assessment window, which is during the first cycle of therapy. The RP2D from this study will be utilized in the Idasanutlin +

Atezolizumab arm in the Phase II portion of this study. The determination of the MTD and RP2D are reviewed in the following table. Of note, the PI may adjust the RP2D based on overall tolerability after cycle 1 at their discretion after discussion with all study Pl's.

Number of Patients with DLT at a given dose level	Escalation Decision Rule
0 out of 3	Enter 3 patients at the next dose level.  If dose level 3 is reached without DLT, then dose level 3 will be considered the MTD and RP2D.
>= 2	Dose escalation will be stopped. This dose level will be declared the maximally administered dose (highest dose administered), exceeding the MTD. Three (3) additional patients will be entered at the next lowest dose level if only 3 patients were treated previously at that dose.
	If this occurs at dose level 1, then 3-6 additional patients will be enrolled on dose level -1, based on toxicity occurring at that dose level. If ≥ 2 patients experience DLT at dose level -1, then the study is considered a failure.
1 out of 3	Enter at least 3 more patients at this dose level. If 0 of these 3 patients experience DLT, proceed to the next dose level. In the event that enrollment is on dose level 3 when this occurs, then dose level 3 is considered the MTD and the RP2D.
1 out of 3	If 1 or more of this group suffer DLT, then dose escalation is stopped, and this dose is declared the maximally administered dose. Three (3) additional patients will be entered at the next lowest dose level if only 3 patients were treated previously at that dose.
≤1 out of 6 at highest dose level below the maximally administered dose	This is generally the MTD and RP2D. At least 6 patients must be entered at the recommended phase 2 dose. These patients will also be considered evaluable in the phase II portion of the study.

#### 24.2. Phase II Trial of Atezolizumab with Cobimetinib or Idasanutlin Study Design

Subsequent to the completion of the Phase Ib dose escalation portion for the Idasanutlin arm of this study, the Phase II portion of the Idasanutlin arm of this trial will open. The Phase II portion of the Cobimetinin arm will start once the study is activated, as no Phase I is necessary for that combination. Patients will be allocated based on TP53 mutational status and treated with a 15 day lead-in of Cobimetinib or Idasanutlin, followed by combination therapy with Atezolizumab until progressive disease or intolerable toxicity. Tumor tissue and blood will be obtained at study start and before initiation of Atezolizumab. Additional blood samples will be obtained after the first cycle of combination therapy and at disease progression.

The primary endpoint of this study is Progression-Free Survival (PFS); imaging will be performed at 8-week intervals. To observe a definitive outcome (success or failure), we will define treatment success as being progression-free at 16 weeks when the subjects will have the second imaging. Patients will be followed for a minimum of 12 months from time of study initiation, and their actual progression-free survival time will be recorded. There will be two treatment groups; however, these two groups will not be compared, rather each arm will be compared to historic control.

Secondary endpoints include ORR defined by iRecist, Clinical benefit rate (lack of disease progression at 6 months), Duration of Response (DOR), Overall Response Rate (ORR by RECIST 1.1), and percentage of patients alive (OS) at 12 months, and will be similarly summarized with 95% CI by arm. Patients will be followed for a minimum of 12 months from time of study initiation.

Safety will be evaluated by estimating the percentage of patients who experience a clinically relevant toxicity (both patient and physician reported) for each arm. Additionally, continuous monitoring for toxicity will be employed.

#### 24.3. Sample Size/ Accrual Rate

## 24.3.1. Primary Endpoint/ Sample Size

In recently reported trials of PD-L1 therapies, the median progression-free survival (PFS) rates of 8 weeks were observed in ER+ mBC. Assuming an exponential survival model, this corresponds to the hazard rate of 0.0866 and progression-free survival of 25% and 13% at 16 and 24 weeks, respectively. For the new treatment arms, we expect the median PFS to be 16 weeks, which corresponds to the hazard rate of 0.0433. The table below summarizes the two survival curves.

Group	Median	Hazard Rate	Proportion Surviving		
	Survival		8 weeks	16 weeks	24 weeks
Historical Control	8 weeks	0.0866	50%	25%	13%
Cobimetinib / Idasanutlin	16 weeks	0.0433	71%	50%	35%

Our proposed phase II trial results will serve as a proof-of-concept for future immunotherapy combination strategies in these patients. In view of the overall low PFS in ER+ mBC treated with single-agent immune checkpoint inhibitors, we opted for an open-label design without an Atezolizumab only control arm, and will use the 16-week PFS (Yes/No) as the primary endpoint. "Response" (16-week PFS and 8-week PFS) will be estimated and reported along with a 95% exact confidence interval. Progression-free survival will be estimated using the Kaplan-Meier method with censoring used as needed (e.g. if a patient is lost to follow-up, or analysis is done before all patients have had the event of interest). Median time to event and corresponding 95% CI will be reported along with Kaplan-Meier curves. The duration of PFS for patients who progress and then subsequently die will be the number of days between initiation of the study treatment and the date of when disease progression is first observed.

We propose to use a Simon's Minimax design with stage I and II sample sizes of 16 and 17. respectively (maximum total of 33 patients per arm), to ensure that the total number of patients exposed to Atezolizumab + Cobimetinib or Idasanutlin is minimized in each of the arms in the trial. The futility boundary at the end of stage I is 4, that is if we have 4 of fewer "responses", then the trial will be terminated. At the end of the trial if there are 13 or more "responses", we will conclude clinical benefit of Cobimetinib or Idasanutlin. This design has 4.5% type I error rate at response rate of 25%, and 90% power if the true "response" rate is 50% or higher. At the end of stage I, patient accrual will not be halted; accrual will be stopped after the data from the 16th patient are available and the number of responders is below the threshold. The patients who are already accrued at the time of interim decision will be followed and their data will be included in all the subsequent analysis.

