The clinical trial associated with this proposal is a multicenter, open-label, 2-arm phase lb/ll trial that will evaluate the anti-tumor effect of Atezolizumab (an anti- PD-L1 mAb) in combination with Cobimetinib (a MEK inhibitor) in patients with TP53-mutated ER+ mBC, or Idasanutlin (an MDM2 antagonist) in patients with *TP53*-wt ER+ mBC. All participants will have targeted Next Generation Sequencing (NGS) performed prior to treatment arm allocation for TP53 mutation status determination and assess tumor mutation burden. We would expect about - 40% of all patients with ER+ mBC to have a TP53 mutation (TP53-mut) in their tumor. Briefly, patient's eligibility criteria will include: ER+ mBC refractory to endocrine therapies with biopsy-accessible tumor, no prior use of MEK, MDM2, PD-1 or PD-L1 inhibitors/ antagonists, no more than 3 lines of chemotherapy in the metastatic setting, ECOG performance status ::1, normal baseline blood counts and chemistry laboratory profile, no concurrent use of immunosuppressive medications,

and no concurrent uncontrolled illness, including autoimmune diseases with reasonable possibility of clinically significant complications. In the phase Ib portion of the trial we will determine the safety and tolerability [Dose Limiting Toxicity (DLT), Maximum Tolerated Dose (MTD) and Recommended Phase II Dose (RP2D) determination] of Atezolizumab and Idasanutlin in patients with ER+ mBC. With three possible dosing cohorts, a minimum of 9 and a maximum of 18 subjects may be recruited for the dose escalation portion of the study. In the phase II portion of the trial we will determine the anti-tumor effect and adverse event profile of Atezolizumab with Cobimetinib or Idasanutlin in patients with ER+ mBC [Progression Free Survival (PFS) and/or Clinical Benefit Rate (CBR; percentage of patients without disease progression at 6 months); immune-related Response Criteria (irRC), Overall Response Rate (ORR; by RECIST 1.1 - for patients with measurable disease), Percentage of patients alive at 12 months (% OS), and Adverse Event profile]. A minimum of 33 and a maximum of 66 patients (total in both arms) will be allocated to receive:

- Arm 1 (TP53-mut) Atezolizumab 840 mg IV, on Days 1 and 15, and Cobimetinib 60 mg PO daily, on Days 1 - 21, every 28 days (on Cycle 1 only Atezolizumab will start on Day 15); or

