## 7. TREATMENT PLAN

## 7.1. Overview

This is a multicenter, open-label, 2-arm phase Ib/II trial that will evaluate the anti-tumor effect of Atezolizumab (an anti- PD-L1 mAb) in combination with Cobimetinib (a MEK inhibitor) in patients with TP53-mutated ER+ mBC, or Idasanutlin (an MDM2 antagonist) in patients with TP53-wt ER+ mBC. In the phase Ib portion of the trial we will determine the safety and tolerability [Dose Limiting Toxicity (DLT), Maximum Tolerated Dose (MTD) and Recommended Phase II Dose (RP2D)] of Atezolizumab and Idasanutlin in patients with ER+ mBC. With three possible dosing cohorts, a minimum of 9 and a maximum of 18 subjects may be recruited for the dose escalation portion of the study. In the phase II portion of the trial we will determine the anti-tumor effect and adverse event profile of Atezolizumab with Cobimetinib or Idasanutlin in patients with ER+ mBC [Progression Free-Survival (PFS), Overall Response Rate (ORR; by RECIST 1.1) and/or Clinical Benefit Rate (CBR; percentage of patients without disease progression at 6 months); immunerelated Response Criteria (irRC), Percentage of patients alive at 12 months (% OS), and Adverse Event profile]. All participants will have targeted Next Generation Sequencing (NGS) performed prior to treatment arm allocation for TP53 mutation status determination and assess tumor mutation burden. We would expect about ~ 40% of all patients with ER+ mBC to have a TP53 mutation (TP53-mut) in their tumor3. For the phase II portion of the trial, a minimum of 33 and a maximum of 66 patients (total in both arms) will be receive study drugs (atezolizumab with cobimetinib or idasanutlin, based on TP53 mutation status) until disease progression. unacceptable adverse event(s), concurrent illness that prevents further administration of treatment, patient withdrawal from study, or significant non-compliance with protocol. To assess the anti-tumor effect of therapy, we will estimate the overall tumor burden at baseline to which subsequent measurements (performed every 8 weeks using the Solid Tumor Response Criteria [RECIST] v1.1) will be compared. Tumor biopsies (fixed for IHC analysis and snap-frozen for RNA extraction) and peripheral blood will be collected prior to initiating Cobimetinib/Idasanutlin (PRE-Bx), and after 15 days of Cobimetinib/Idasanutlin, prior to adding Atezolizumab (POST-Bx).

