# 7.6. Definition of Maximum Tolerated Dose (MTD) – for patients on idasanutlin arm only

The MTD will be defined as the highest dose tested in which a DLT is experienced by 0 out of 3 or 1 out of 6 patients among the dose levels. The first cohort of patients (3 patients) will be started at dose level 1, and each patient will be observed for 6 weeks on the specified dose:

If no patient in the first cohort of 3 experiences a DLT, accrual will continue to test the next dose level
If 1 patient experiences a DLT any given cohort/ dose level, an additional cohort of 3 patients will be treated at the same dose level
If 1 patient has a DLT out of 6 patients treated at this same dose, accrual will continue to test the next dose level
If 2 or more patients in 3 or 6 patients treated at a given dose experience DLT, the dose will be de-escalated to the next lower dose level. If the current dose level is at -1, the regimen will be considered too toxic and the corresponding cohort within the study will be discontinued
If 0 out of 3 or 1 out of 6 patients has a DLT treated at dose level 3, accrual will continue to the phase II portion of the study

No new cohort of patients will be treated until the previous cohort has been fully evaluated for toxicity and a dose escalation decision has been made. Routine updates regarding patient and study status will be conducted.

Once the MTD is reached, the expansion component of the study will be completed to assess tolerability and efficacy. Patients in the phase II portion of the study will initiate study treatment at the MTD defined in the escalation component of the trial. Note that dose reduction within patients (individually) is allowed after the 4 week DLT observation period in the escalation and in the expansion components of the study (see Dose Modification guidelines, Section 8). Intrapatient dose escalation will not be allowed. Dose reduction will be required for a given patient in case of:

- ☐ Grade 3 or 4 toxicities
- Grade ≥ 2 elevation of creatinine, bilirubin, AST, or ALT lasting more than 14 days despite medical treatment, or
- Grade ≥ 2 ocular, skin or nail toxicity for more than 28 days in a row despite optimal medical treatment, or
- Grade ≥ 2 GI toxicity lasting more than 14 days despite medical treatment.

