#### 7.12. **Replacement of Patients Who Discontinue Early**

In general, the study intends that patients would be treated until disease progression or intolerable toxicity. If a patient discontinues study treatment for reasons clearly not related to study treatment, after completing fewer than one planned cycle of study, and/or receiving <75% of the total intended dose of study drugs over the first cycle of treatment, then that patient will be considered not evaluable for efficacy analysis (will still be included in the safety analysis though) and may be replaced with a new patient.

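### The Section 7.4 treatment table lists 40 Phase II patients in each arm, but the Simon design in Section 24.3.1 allows at most 33 per arm

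*Combined protocol and SAP*

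**What the plan says.** Section 24.3.1 gives the design: "We propose to use a Simon's Minimax design with stage I and II sample sizes of 16 and 17". The same sentence then sets the ceiling for each arm: "respectively (maximum total of 33 patients per arm". An arm stops for futility at 4 or fewer responses among the first 16, and benefit is concluded at 13 or more at the end. A response here means being progression-free at 16 weeks. The section states a 4.5% type I error at a true rate of 25% and 90% power at 50%.

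The overall Phase II size follows from this. Section 1 says: "A minimum of 33 and a maximum of 66 patients (total in both arms) will be allocated to receive". Section 7.1 repeats the range: "a minimum of 33 and a maximum of 66 patients (total in both arms". The synopsis also gives a Phase II maximum of 66.

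The dose table in Section 7.4 has a column for the number of patients. Its two Phase II rows, cobimetinib and idasanutlin, each show 40.

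**The concern.** The protocol carries two different Phase II sizes: 33 per arm in the statistical section and 40 per arm in the treatment table. Neither refers to the other. The 40 is not described as an allowance for dropout, for replacement or for patients enrolled while the stage I result is awaited.

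This matters more than an ordinary table slip because the success criterion is a count, not a proportion. Thirteen of 33 and 13 of 40 are different hurdles. A reader who takes enrolment from Section 7.4 and the decision rule from Section 24.3.1 would combine two figures that do not belong together. Section 24.3.1 also gives limiting patient exposure as a reason for the design, and 40 per arm would work against that.

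**Working it through.** **Inputs.** From Section 24.3.1: n1 = 16; continue if more than 4 responses; N = 33; success at 13 or more in total; p0 = 0.25; p1 = 0.50. From the Section 7.4 table: 40 per arm. From the synopsis and Sections 1 and 7.1: Phase II maximum 66.

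**Null and target rates.** Under the plan's exponential model, 16-week PFS is exp(−0.0866 × 16) = 0.250 for the historical control and exp(−0.0433 × 16) = 0.500 for the new combinations. Both agree with the plan.

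**Formula.** With X1 ~ Bin(16, p) and X2 ~ Bin(N − 16, p), the probability of declaring success is the sum, over x = 5 to 16, of P(X1 = x) × P(X2 ≥ c − x), where c is the final cut-off. Setting p = 0.25 gives the type I error and p = 0.50 the power.

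**The plan's own figure.**

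| N per arm | Cut-off c | Type I error | Power |
|---|---|---|---|
| 33 | 13 | 4.49% | 90.2% |

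This matches the printed 4.5% and 90%. A search over designs with type I error at most 5% and power at least 90% returns 33 as the smallest possible maximum. Among designs of that size, 16 patients with a stage I boundary of 4 has the lowest expected sample size under the null (22.3). Section 24.3.1 is therefore correct as a minimax design.

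**Totals.** 2 × 33 = 66, as in the synopsis and Sections 1 and 7.1. 2 × 40 = 80. The difference is 14 patients, and 80 / 66 = 1.21.

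**What the count of 13 would do at other sizes, keeping the stage I rule.** These rows are conditional; no section prescribes them.

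| N per arm | Cut-off c | Type I error | Power |
|---|---|---|---|
| 34 | 13 | 5.5% | 91.9% |
| 40 | 13 | 13.7% | 95.7% |
| 40 | 14 | 8.5% | 95.0% |
| 40 | 15 | 4.8% | 93.4% |

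One patient beyond 33 already takes the type I error above 5%. A 40-patient arm would need a cut-off of 15.

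**Accrual plan (Section 24.3.2).** A linear rise to 4 per month over 6 months gives ½ × 6 × 4 = 12 patients. The remaining 18 months give 18 × 4 = 72, so 84 in all. That equals 66 plus the Phase Ib maximum of 18. The accrual plan fits 66 and does not need 80.

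**The minimum of 33.** If both arms stop at stage I, the nominal floor is 2 × 16 = 32. The figure 33 equals one arm's maximum (16 + 17), but the protocol does not say how the two-arm minimum was obtained.

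**The case against.** The strongest reply is that four places (the synopsis, Sections 1, 7.1 and 24.3.1) agree on 33 or 66, that the total of 80 is printed nowhere, and that one dose table does not govern the analysis. All of that stands. It shows which figure is the outlier and makes the correction easy, but it does not explain the 40. A dropout allowance of about 17.5% would turn 33 into 40 (33 / 0.825 = 40), yet the protocol states no dropout rate. Amendment 4 revised the primary endpoint and statistical considerations, so the 40 may be left over from a previous design; that is plausible but cannot be shown from the text.

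Two stronger readings are tempting, and the documents support neither.

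- *That the trial has a 13.7% type I error.* This needs the count of 13 to be applied to 40 patients. Section 24.3.1 ties it to 16 + 17, and there the error rate is as stated.
- *That the minimum of 33 is an arithmetic error for 32.* Section 24.3.1 says "At the end of stage I, patient accrual will not be halted", so an arm that stops for futility can exceed 16, and one extra patient makes 33. In the other direction, Section 7.6 provides that if dose level −1 proves too toxic "the corresponding cohort within the study will be discontinued", in which case the idasanutlin arm might never open Phase II. Thirty-two is therefore only a nominal floor. What can be said is that the basis for 33 is not given.

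**Conclusion.** The contradiction is real and confined to the Section 7.4 table: 40 per arm against a design maximum of 33, or 80 against 66 in total. The statistical section is sound and its operating characteristics reproduce exactly. The stated 4.5% and 90% belong to 13 or more out of 33. The inflation to 13.7% is a conditional illustration of why the 40 should not stand beside a fixed-count rule; it is not a property of the trial as planned. The calculation rests on the plan's own 25% and 50% rates, independent binomial outcomes, and the stage I rule applied at 16 patients. The unexplained minimum of 33 is a minor point of wording.

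**What to change.** 1. In the Section 7.4 table, change both Phase II entries from 40 to 33.
2. In Section 24.3.1, state that the 13-or-more rule applies to 33 patients per arm and that any other final number needs its own cut-off.
3. Wherever the two-arm minimum of 33 appears, say how it is counted: whether it includes patients accrued while stage I outcomes are awaited, and whether it assumes that both arms open.

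The cost is a table and wording correction. The design, the boundaries and the maximum of 33 per arm do not change.

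Two neighbouring matters need reconciling separately and should not be folded into this edit. Section 7.12 makes some early discontinuers non-evaluable for efficacy, each of whom "may be replaced with a new patient", whereas Section 25 keeps eligible patients in the main response analysis and counts those who cannot be assessed as failures; Sections 7.10 and 7.11 also bear on this. Choosing between these rules could change who counts toward the 13, so it is not a wording change. Section 24.1 says of patients treated at the recommended Phase II dose in Phase Ib: "These patients will also be considered evaluable in the phase II portion of the study". It does not say whether they fall inside the 33.

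### Stage I futility: accrual to an arm waits for the 16th patient's data although 12 failures among the first 16 already settle the stop, and the later stopping sentence should state the number 4

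*Combined protocol and SAP*

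**What the plan says.** All the relevant text is in section 24.3.1 (Primary Endpoint/ Sample Size). Each arm follows a "Simon's Minimax design with stage I and II sample sizes of 16 and 17", with at most 33 patients. Success is being progression-free at 16 weeks.

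The stage I rule appears twice:

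- With a number: "The futility boundary at the end of stage I is 4, that is if we have 4 of fewer" successes are seen, "then the trial will be terminated".
- Without a number, for the timing: "At the end of stage I, patient accrual will not be halted", and then "accrual will be stopped after the data from the 16th patient are available and the number of responders is below the threshold".

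Patients already enrolled at the decision are followed and analysed. The final rule declares benefit at 13 or more successes. The stated operating characteristics are 4.5% type I error at a 25% success rate and 90% power at 50%.

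No section provides for stopping an arm whose stage I result is already determined. Sections 20 and 21 (meetings, monitoring) and 22.6 (study termination) give only general oversight and termination powers.

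**The concern.** Failures on this endpoint become known before successes do. Section 24.2 schedules imaging every 8 weeks, and the null model in section 24.3.1 has half the patients progressed by week 8. A success cannot be confirmed until week 16. The count that settles futility can therefore be reached while several of the 16 patients are still under observation. As written, the arm keeps enrolling through that interval, and each patient added then enters an arm that is bound to stop.

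The second matter is wording. The timing sentence refers to a threshold that is not defined there. The paragraph gives one stage I number, a futility boundary of 4. A literal reader could take responders below the threshold to mean 3 or fewer, which differs from the numeric rule at exactly 4 of 16. That count has a 22.5% probability under the null, so the person applying the rule should not have to infer it.

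**Working it through.** **Inputs from the documents.** n1 = 16, n = 33, stop at ≤ 4, benefit at ≥ 13, p0 = 0.25, p1 = 0.50 and null median PFS 8 weeks (24.3.1). Scans every 8 weeks, success judged at week 16 (24.2). Accrual of 4 per month over both arms (24.3.2). About 40% *TP53*-mutated (7.1).

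**1. The plan's own figures.** Let X be stage I successes.

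P(benefit) = Σ over x = 5…16 of P(Bin(16, p) = x) × P(Bin(17, p) ≥ 13 − x)

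- p = 0.25: 0.0449, matching the stated 4.5%.
- p = 0.50: 0.9017, matching the stated 90%.
- P(X ≤ 4) at 0.25 = 0.630; expected N = 16 + 17 × (1 − 0.630) = 22.3.

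An exhaustive search (type I error ≤ 0.05, power ≥ 0.90) confirms 16/33 with boundaries 4 and 12 as the minimax design.

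**2. When the stop is settled.** 16 − 12 = 4, so after 12 failures at most 4 successes are possible. Taking outcomes in patient order at p = 0.25:

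P(12th failure is patient k) = C(k − 1, 11) × 0.75^12 × 0.25^(k − 12)

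| k | 12 | 13 | 14 | 15 | 16 |
|---|---|---|---|---|---|
| Probability | 0.032 | 0.095 | 0.154 | 0.180 | 0.169 |

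The sum is 0.630, the same stopping probability as in step 1. Stopping at the 12th failure therefore gives the same stop-or-continue decision, and type I error and power are unchanged. The probability of reaching it before patient 16 is 0.461, and 0.461/0.630 = 73% of futility stops.

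**3. Calendar time under the null.** Assumptions: per-arm accrual 4 × 0.40 = 1.6 and 4 × 0.60 = 2.4 per month; exponential PFS with hazard ln 2/8 = 0.0866 per week; failures seen at the week 8 or week 16 scan; immediate reporting; random (Poisson) arrivals; 40,000 runs per rate. Means in arms that stop:

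| Per month | Enrolled at 12th failure | Enrolled when patient 16's outcome is known | Enrolled when all 16 are known | Week of 12th failure | Week all 16 are known |
|---|---|---|---|---|---|
| 1.6 | 18.8 | 20.3 | 21.0 | 51.1 | 57.3 |
| 2.0 | 19.9 | 21.4 | 22.4 | 43.2 | 48.6 |
| 2.4 | 21.0 | 22.4 | 23.8 | 38.2 | 43.2 |

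The sentence can mean patient 16's own outcome or the completed set of 16, so both are shown. The extra enrolment runs from 22.4 − 21.0 = 1.4 (patient 16's own outcome, 2.4 per month) to 23.8 − 21.0 = 2.8 (all 16, 2.4 per month). Against the completed set, the decision comes 5.0 weeks (2.4 per month) to 6.2 weeks (1.6 per month) earlier, and the 12th failure comes first in about 80 to 83% of futility stops.

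**4. What hangs on the count 4.** At p = 0.25, P(X = 4) = 0.225. An arm continuing from 4 needs 9 of 17, with probability 0.0124.

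| Stop at | Type I error | Power | Early stop at 25% | Expected N at 25% |
|---|---|---|---|---|
| ≤ 4 | 0.0449 | 0.9017 | 63.0% | 22.3 |
| ≤ 3 | 0.0477 | 0.9156 | 40.5% | 26.1 |

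Check: 0.0449 + 0.225 × 0.0124 = 0.0477, and 63.0% − 22.5% = 40.5%. Only ≤ 4 agrees with the stated 4.5%.

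**The case against.** **Waiting for all stage I outcomes is how a Simon look is defined.** This stands. The plan openly chooses not to halt accrual and says how over-run patients are handled. A reader might infer that the design breaks its own promise to keep exposure low. The text does not support that: the aim is stated as the reason for a minimax design with at most 33 per arm, and minimax minimises the maximum sample size, which this design does.

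**The saving is small.** This also stands.

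- The 1.4 to 2.8 patients apply only to arms that stop. Averaged over all null arms, waiting for all 16 costs about 0.63 × 2.25 = 1.4 (1.6 per month) to 0.63 × 2.78 = 1.8 (2.4 per month). At a true 50% rate, where 3.8% of arms stop, it is about 0.1.
- About 30 to 35% of futility stops would save no patient.
- Most over-run comes from not pausing accrual: 16 weeks after the 16th entry adds about 5.9 patients at 1.6 per month and 8.8 at 2.4. Even with the change, 18.8 to 21.0 patients are enrolled when the arm stops.

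**The wording at 4 resolves itself.** Largely so. A reader might infer that the plan contains two conflicting boundaries. But threshold could mean the 5 successes needed to continue, in which case the sentences agree, and the numeric rule together with the stated 4.5% identifies 4 or fewer. What remains is a missing number.

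**Does futility in one arm end both?** A reader might infer this from the word trial in the stopping sentence. The context rules it out: sample sizes are set per arm, section 24.2 compares each arm separately with historical control, and the next sentence uses the same word for a 13-success rule that only fits one 33-patient arm.

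**Conclusion.** The point holds as an inexpensive improvement plus a clarification. The plan keeps enrolling to an arm after its stage I result can be certain. Under the null this adds about 1.4 to 2.8 patients to an arm that stops, which 63% of null arms do, and delays the decision by about 5 to 6 weeks if all 16 outcomes are awaited. Those sizes rest on the assumed accrual split, exponential PFS and prompt scan reporting. The certainty at 12 failures and the figures for 4 versus 3 are exact. The 12-failure count itself relies on the 4-or-fewer rule, which the stated type I error supports.

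The documents do not support calling the rule wrong, the 4.5% and 90% misstated, or the two arms tied to each other.

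**What to change.** Replace the timing sentence in section 24.3.1 with: *In each arm separately, accrual to that arm stops as soon as 12 of its first 16 patients are known failures on 16-week PFS (so that at most 4 successes are possible); it continues if 5 or more of the 16 succeed.* This supplies the missing number and makes the per-arm scope explicit.

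Two details belong with it. Known failure should have the same definition as in the planned stage I look. For the idasanutlin arm, the text should say whether the phase Ib patients treated at the recommended dose, whom section 24.1 counts as evaluable in phase II, are among the first 16.

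The cost is one sentence of protocol text and a running failure count per arm, which the monthly reviews and site teleconferences in section 20 can carry. Type I error, power and the maximum of 33 are unchanged. A stopped arm contributes slightly fewer patients to secondary and correlative estimates.

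The same logic could be extended to the end of the study (21 failures of 33 rule out 13 successes). I would not recommend it, because it costs precision on the secondary and correlative endpoints.
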